8.3.2 Relationship of Study Device and/or Procedure

The causal relationship to study device and/or procedure will be evaluated as follows:

Caused By	Relation	Definition of Relation
	Definitely Related	The event is clearly related to the study device beyond reasonable doubt.
Study Device	Probably Related	The event is temporally associated and plausibly related to the study device but there are also potential alternative explanations, though the alternatives are not likely.
	Possibly Related	The adverse event may be related, scientifically plausible to the study device, but there are also alternative explanations.
	Definitely Related	The event is clearly related to the procedure beyond reasonable doubt.
Procedure	Probably Related	The event is temporally associated and plausibly related to the procedure but there are also potential alternative explanations, though the alternatives are not likely.
	Possibly Related	The adverse event may be related, scientifically plausible to the procedure, but there are also alternative explanations.

8.3.3 Outcome of Event

The outcome of each Device and/or Procedure Related Adverse Event must be assessed according to the following classifications:

Classification	Definition
Resolved	Subject fully recovered with no observable residual effects
Resolving	Subject's condition improved, but residual effects remain

DWF-C0001-001 CONFIDENTIAL Page 32 of 44

Resolved with Sequelae	Subject recovered with observable residual effects
Ongoing	Event is ongoing without changes in the overall condition
Fatal	Subject died as a result of the device and/or procedure related event

8.4 Reporting Procedures

All UADE/SADE/SAEs must be recorded and reported to the Sponsor via the eCRFs throughout the study, *immediately upon study site staff awareness of the event but not later than 72 hours by the study site personnel.* In the event the EDC is unavailable, events can be reported via email to the Sponsor study mailbox: [contact] and/or to the study Sponsor contact. Note: The event will still need to be recorded on the eCRFs once the EDC is functional.

In case device malfunctions occur, they will be reported to NovaSignal within 10 business days. The report should include at a minimum, a description of event, date of occurrence, lot or serial number of the device.

Timing for the reporting for the different types of AEs and Device Deficiencies is described as follows:

Classification	Reporting time	Type of report
Unanticipated Adverse Device Effects (UADE)	Notify NovaSignal immediately upon study site staff awareness of event but not later than 72 hours. Notify IRB as required.	Device/Procedure Related Serious Adverse Event Report Form
Serious Adverse Events (SAE) or Serious Adverse Device Effect (SADE)	Notify NovaSignal immediately upon study site staff awareness of event but not later than 72 hours. Notify IRB as required.	Device/Procedure Related Serious Adverse Event Report Form
Study Device Deficiency/Malfunction With or Without AE	Notify NovaSignal within 10 business days of learning of event. Notify IRB as required.	Device Deficiency/ Malfunction Form

9 PROTOCOL DEVIATIONS

A protocol deviation is defined as a failure to comply (intentionally or unintentionally) with the requirements of the clinical study as specified in the protocol.

Examples of deviations include but are not limited to a required test not being done or not being done within the specified timeframe, a subject enrolled who did not meet the inclusion/exclusion criteria, or enrolment of a subject without appropriate consent.

Deviations from the protocol must be reported to NovaSignal through the eCRFs and will be reviewed and assessed by the Sponsor.

DWF-C0001-001 CONFIDENTIAL Page 33 of 44

The site is responsible to use vigilance to identify and report deviations to the Sponsor and per site IRB policies. The study monitors shall verify that the conduct of the study is in compliance with the approved protocol and applicable regulations and shall identify deviations and any issues of noncompliance. Corrective and preventative actions will be implemented promptly and as necessary. Significant protocol deviations that raise subject safety concerns or indicate repeat noncompliance may be grounds for investigator disqualification.

The Investigator must provide reports of the progress, completion, termination or discontinuation of the study to the IRB(s) at appropriate intervals as designated by the Sponsor and per IRB requirements.

10 QUALITY CONTROL AND QUALITY ASSURANCE

10.1 Organizational Preparations

A site evaluation via personnel and facility documentation will be performed by NovaSignal or their designee during the study to ensure the availability of appropriately trained personnel to conduct the study according to the FDA Code of Federal Regulations and ICH Guidelines on Good Clinical Practices (ICH-E6). This study will be conducted under the principles described in the Declaration of Helsinki.

10.2 Training

NovaSignal will provide training for the use of the NeuralBot Investigational System, in adherence to the Instructions for Use/User Manual. Documentation of training should be maintained by the Principal Investigator throughout the study.

10.3 Data Quality Assurance

Training of appropriate site personnel will be the responsibility of NovaSignal or designee. To ensure uniform data collection and protocol compliance, site personnel will utilize source documentation worksheets to document protocol procedures. Principal investigators will assist in developing training modules for standardization of clinical technique.

10.4 Subject Privacy

All data will be maintained under highly secure and fully HIPAA-compliant dedicated servers under the direction supervision of the Principal Investigator. Primary data that is obtained will have identifying information and will be stored securely onsite. Access to identifiable subject data is limited to project staff who have direct data management and/or statistical responsibilities, under the direct supervision of the Principal Investigator.

The study participant's contact information will be securely stored at each clinical site for internal use during the study. At the end of the study, all records will continue to be kept in a secure location for as long a period as dictated by the reviewing IRB.

Data de-identification will be performed manually using the "safe-harbor" approach under the supervision of the Principal Investigator. At this point, a unique ID is generated for each subject, and each exam. These will populate two databases using the "safe-harbor" approach under the supervision of the Principal Investigator. The database that is devoid of all PHI will be used for data analysis in this research.

DWF-C0001-001 CONFIDENTIAL Page 34 of 44

10.5 Case Report Forms

All required data for this study will be collected on standardized Case Report Forms (CRF). The forms may be paper based or electronic. The forms will only include the subject study number assigned once the subject is screened. The investigator is responsible for the accuracy, completeness and legibility of the data reported to NovaSignal in the CRFs and in all required reports. The CRFs are to be dated and signed by an investigator on appropriate pages to verify that he/she has reviewed the recorded data.

10.6 Investigational Device Accountability

The NeuralBot Investigational System specific serial numbers must be documented at a study site by a designated person, handled and stored properly in a secured location in which only the study staff have access. The Principal Investigator must maintain an accurate record of the status of the products throughout the study. Investigators are responsible for appropriate logging of the devices used, verification of packing slip information (i.e. lot numbers and quantity shipped), date and identity that each device was used in the study, disposition information regarding disposal or return to the Sponsor.

10.7 Selection of Investigators

The study will be conducted at multiple centers. Study staff for each center will meet the following criteria:

- A user trained by NovaSignal in the use of the Lucid M1 System and NeuralBot Investigational System.
- Commitment from the participating investigator to pursue details of any potentially device and procedure related adverse event outcomes.
- Commitment from the participating investigator to enroll only subjects meeting inclusion and exclusion criteria of the local approved protocol.
- Dedicated staff members who can collect and transmit data and be willing to maintain all study-related documentation (e.g., source documents, CRFs, regulatory documentation, etc.)

10.8 Close-out Document Review

The purpose of the final document review is to collect all outstanding study data documents, ensure that the principal investigator's files are accurate and complete, review record retention requirements with the principal investigator and ensure that all applicable requirements are met for the study.

The investigator agrees to allow the monitoring of study data, the completion of all data clarification or audits even after study close-out visit has been performed at NovaSignal's request.

11 STATISTICAL ANALYSIS

11.1 Primary Endpoint Analysis

- Demonstration of NB-IS TCD diagnostic performance for shunt detection, as compared to transthoracic echocardiography (TTE) for diagnostic accuracy.
 - Diagnostic Accuracy Shunt detection rate (%)

> % detection of true positives (TP) (sensitivity), all sample size estimations will be computed with regard to the endpoint of sensitivity

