2.3 Limitations

Although TTE is the most frequently used non-invasive technique for the assessment of RLS, it is limited by its dependence on the expertise of the technician performing the exam. Furthermore, its moderate sensitivity (45.1%) but high specificity (99.6%) in RLS indication should not be relied upon in the determination of treatment for ESUS patients⁶.

While TEE is considered the gold standard for visualization of the PFO after its presence has been indicated, its invasive nature can make it difficult for the patient to comply with the necessary steps for the VM. Although TEE is contraindicated in patients with dysphagia or esophageal issues, its sensitivity and specificity are 95% and 95% for indication of RLS⁷.

Like TTE, the diagnostic value of TCD is limited by the expertise of the technician performing the exam and the presence of optimal acoustic windows. Signal acquisition is a well-documented obstacle in TCD evaluation regardless of pathology and is no different in the case of RLS

DWF-C0001-001 CONFIDENTIAL Page 14 of 44

assessment⁸. However, unlike TTE, TCD has shown excellent sensitivity and specificity in RLS detection (96.1% and 92.4%, respectively) against the gold standard of TEE⁶.

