4.1 Primary Efficacy Endpoint

 % detection of RLS/PFO with NB-IS TCD compared against standard of care Transthoracic Echocardiography (TTE)

4.2 Secondary Technical Efficacy Endpoints:

- % agreement for detection of RLS/PFO with NB-IS TCD vs SOC TCD
- % agreement for detection of RLS/PFO with NB-IS TCD vs Transesophageal Echocardiography (TEE)
- % agreement for detection of clinically significant shunts with NB-IS TCD vs TTE
- No window rate (including both unilateral and bilateral absent acoustic windows)
- Success rate of the NB-IS TCD
- Incidence of NB-IS device malfunctions

4.3 Exploratory Endpoints:

 Development of an automated algorithm for Spencer Logarithmic Scale¹⁰ and International Consensus Criteria grading of RLS¹¹

4.4 Primary Safety Endpoint:

Incidence of device-related serious adverse events.

4.5 Secondary Safety Endpoints:

Incidence of procedure-related adverse events related to agitated saline injection before and after VM (headache, allergic reactions, new onset neurological deficit, ischemic stroke, TIA or

DWF-C0001-001 CONFIDENTIAL Page 18 of 44

pulmonary embolism complicating agitated saline contrast injection, etc) will be closely monitored and prospectively collected¹².

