6.5 Study Schedule

6.5.1 Schedule of Assessments

Schedule of Assessments					
Assessments	Screening ¹	Procedure ¹	Follow-Up ¹		
Informed Consent	х				
Demographics	Х				
Relevant Medical History	Х				
Physical Exam ◆	Х				
SOC TCD Bubble Study Exam ◆		O ⁴			
NB-IS TCD Bubble Study Exam		X ²			
Transthoracic Echocardiograph (TTE) Bubble Study ◆		X ³			
Transesophageal Echocardiograph (TEE) ◆		O ⁴ / X ⁸			
PFO Closure Decision ◆			X ⁵		
Classification of Potential Causative Mechanism in PFO–Associated Stroke ⁷ ♦			Х		
PFO Closure Procedure ◆			O _e		
Device-Related Adverse Events		Х			
Procedure-Related Adverse Events		х			
Concomitant Medications	х	х			
Device Deficiencies		Х			

- ♦ Standard of Care X = Required O = Optional, if performed
- 1. Screening, Procedure, and Follow-Up Visits can occur on the same day
- 2. NB-IS TCD performed with contrast agent of 9 ml bacteriostatic saline with 1 ml air mixed 10 times. Performed at Rest AND with VM 60 sec recordings each in supine positions AND with HOB raised to 45 degrees.
- 3. TTE can be performed within ±30 days of informed consent per SOC.
- 4. SOC TCD and TEE results collected if performed as applicable per standard of care.
- 5. PFO closure decision collected post diagnostic imaging procedures.
- 6. PFO closure procedure data collected within 60 days post diagnostic workup, if performed
- 8. SOC TTE or TEE will be required after the first 150 TTE subjects are enrolled and can be performed within ±30 days of informed consent per SOC.

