11.2 Secondary Technical Efficacy Endpoint(s) Analysis

- % detection of false positives (FP), comparison of NB-IS TCD with TTE
- % detection of true negatives (TN) (specificity), comparison of NB-IS TCD with TTE
- % detection of false negatives (FN), comparison of NB-IS TCD with TTE
- Positive Predictive Value (PPV), comparison of NB-IS TCD with TTE
- Negative Predictive Value (NPV), comparison of NB-IS TCD with TTE
- Demonstration of NB-IS TCD diagnostic performance to SOC TCD for diagnostic accuracy parameters (sensitivity, specificity, PPV, NPV).
 - o If bilateral signals are found, the microbubble count will be sum across both vessels.
 - o If only a unilateral signal is found, the microbubble count will be doubled for the total count.
 - Spencer Logarithmic Scale (SLS) and International Consensus Criteria (ICC) gradings from the Imaging Core Lab for NB-IS TCD and SOC TCD will be compared for analysis.
- Demonstration of NB-IS TCD diagnostic performance targeting to transesophageal echocardiography (TEE) for diagnostic accuracy parameters (sensitivity, specificity, PPV, NPV).
- % detection of intervenable shunts, comparison of NB-IS TCD with TTE
 - For NB-IS TCD, Grade 3 and above (>30 microbubbles) on the Spencer Logarithmic Scale (SLS) and International Consensus Criteria (ICC) considered intervenable shunt¹⁰.
 - o For TTE, >20 microbubbles per 2016 American Society of Echocardiography Guidelines and Standards²³ considered intervenable shunt.
- NB-IS TCD No Window rate performance to SOC TCD parameters (including both unilateral and bilateral absent acoustic windows).
- % success rate of NB-IS TCD
 - o Incidence of failed registrations (device unable to register)
 - Incidence of bilateral signals not found (no evaluable signals found both sides)
 - Incidence of unilateral signals not found (evaluable signal found on one side)
 - An adequate, evaluable, and complete study is defined for the purposes of this protocol as successful acquisition of a unilateral signal at 40-65mm depth range recorded for the duration of the bubble study in the Resting position and with Valsalva Maneuver.
- Incidence of device malfunctions

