11.4 Imaging Core Lab Analysis

All de-identified imaging data will be sent to a core laboratory which will provide independent quantitative and qualitative assessment of all NB-IS TCD and SOC TCD, TTE, and TEE bubble study data. They will be blinded to the study and local diagnostic report data and provide independent review. The Core Lab interpretations will supersede all local interpretations and will be applied to all study endpoint analyses as applicable.

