11.5 RLS/PFO Validation and Analysis

Evaluation of correlation between diagnostic imaging standard of care (SOC TCD/TTE/TEE) and NB-IS TCD diagnostic performance by an independent core laboratory. Success criteria will include clinical validation of NB-IS TCD for RLS/PFO detection targeting (i) 40% increase in NB-IS TCD sensitivity compared to TTE sensitivity and (ii) NB-IS TCD sensitivity ≥ 90% compared to SOC TCD sensitivity.

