11.6 Sample Size Calculation

The present study was powered based on the results of a recent meta-analysis reporting a pooled TCD sensitivity of 96.1% for RLS detection, while the pooled TTE sensitivity was estimated at 45.1% (absolute difference of 51%)⁶. For power calculations, we used a more moderate effect size of 40% increase in the sensitivity of NB-IS TCD compared to TTE.

A sample size of 100 subjects achieves 90% power to detect a difference of 40% between two diagnostic tests whose sensitivities are 90% (TCD) and 50% (TTE). This procedure uses a two-sided McNemar test with a significance level of 0.05. The mean prevalence of PFO in the population of patients with cryptogenic stroke is at least 30%². The proportion of discordant pairs has been set at 0.500.

[figure not shown]
		Sensitivity	ity Sensitivity Proportion					
		of Test 1	of Test 2		Discordant	Prevalence		
Power	N	Se1	Se2	Se1-Se2	D	Р	Alpha	Beta
0.00000	10	0.900	0.500	0.400	0.500	0.300	0.05000	
	1.00000							
0.00830	20	0.900	0.500	0.400	0.500	0.300	0.05000	
	0.99170							
0.12990	30	0.900	0.500	0.400	0.500	0.300	0.05000	
	0.87010							
0.32013	40	0.900	0.500	0.400	0.500	0.300	0.05000	
	0.67987							
0.49003	50	0.900	0.500	0.400	0.500	0.300	0.05000	
	0.50997							
0.62345	60	0.900	0.500	0.400	0.500	0.300	0.05000	
	0.37655							
0.72404	70	0.900	0.500	0.400	0.500	0.300	0.05000	
	0.27596							
0.79937	80	0.900	0.500	0.400	0.500	0.300	0.05000	
	0.20063							
0.85654	90	0.900	0.500	0.400	0.500	0.300	0.05000	
	0.14346							
0.89995	100	0.900	0.500	0.400	0.500	0.300	0.05000	
	0.10005							
0.93182	110	0.900	0.500	0.400	0.500	0.300	0.05000	

DWF-C0001-001 CONFIDENTIAL Page 37 of 44

Protocol ID: NA-07BBL-01 Version Date: August 2, 2021

	0.06818						
0.95405	120	0.900	0.500	0.400	0.500	0.300	0.05000
	0.04595						
0.96898	130	0.900	0.500	0.400	0.500	0.300	0.05000
	0.03102						
0.97890	140	0.900	0.500	0.400	0.500	0.300	0.05000
	0.02110						
0.98561	150	0.900	0.500	0.400	0.500	0.300	0.05000
	0.01439						

 $\label{eq:vsN} vs~N$ Se1=0.900 Se2=0.500 D=0.500 α =0.050 P=0.300 2-Sided McNemars Test

Given previous reports indicating a prevalence of suboptimal transtemporal windows in 5% of Hispanic²⁰, 5% of Caucasian²¹, 9% in African American¹⁹ and 14% of Asian²² individuals aged <60 years, we increased our projected sample size by 20% (n=120). In addition, the final sample size

DWF-C0001-001 CONFIDENTIAL Page 38 of 44

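### The primary comparison is defined, judged and powered as a sensitivity difference between NB-IS TCD and TTE, but the plan assigns and requires no reference for true shunt status

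*Combined protocol and SAP*

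**What the plan says.** The primary endpoint in Section 4.1 is the percentage "detection of RLS/PFO with NB-IS TCD compared against standard of care Transthoracic Echocardiography (TTE"). It is not conditional on having a shunt. Section 11.1 lists shunt detection rate and then defines the analysis as "detection of true positives (TP) (sensitivity), all sample size estimations will be computed with regard to the endpoint of sensitivity". It does not reconcile the two.

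Success criterion (i) in Section 11.5 is a "40% increase in NB-IS TCD sensitivity compared to TTE sensitivity". Section 11.6 powers a "difference of 40% between two diagnostic tests whose sensitivities are 90% (TCD) and 50% (TTE") with a two-sided McNemar test, 30% prevalence and a discordant proportion of 0.500.

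On who truly has a shunt:

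- Section 2.3, which is background, says "While TEE is considered the gold standard for visualization of the PFO after its presence has been indicated".
- Footnote 4 of the schedule in Section 6.5.1 says "SOC TCD and TEE results collected if performed as applicable per standard of care". Footnote 8 accepts either TTE or TEE after the first 150 TTE subjects.
- Sections 4.2 and 11.2 use TEE only as a secondary comparator for NB-IS TCD.
- Section 11.4 says "The Core Lab interpretations will supersede all local interpretations and will be applied to all study endpoint analyses as applicable". That settles who reads each exam, not which exam decides truth.
- Section 11.2 lists "detection of false positives (FP), comparison of NB-IS TCD with TTE", with matching lines for true negatives, false negatives, PPV and NPV.

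**The concern.** Sensitivity is a proportion among subjects who have the condition. To compare the sensitivities of two tests, a third source must say who those subjects are. Here there is none for the primary comparison, so the analysis in 11.1 cannot be run as written for subjects without TEE.

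The error, false-positive and predictive-value lines in 11.2 imply that TTE is the truth. TTE would then have 100% sensitivity by construction, which contradicts the 50% in 11.6 and makes a 40-point gain over TTE impossible.

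At stake is the main claim of a study labelled pivotal. Criterion (i) and the stated power both rest on a denominator that the plan does not supply. If the detection rate of 4.1 is used instead, the 40-point threshold belongs to another scale.

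**Working it through.** **Inputs.** From 11.6: sensitivities 0.90 and 0.50, prevalence 0.30, discordant proportion 0.50, two-sided alpha 0.05. Among true-shunt subjects this gives 0.45 NB-IS positive/TTE negative and 0.05 the reverse. From 2.3: specificity 0.924 for TCD and 0.996 for TTE; TEE sensitivity and specificity both 0.95. Errors are assumed independent given shunt status, and NB-IS is assumed to have the cited TCD specificity.

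**1. The plan's power.** True-shunt subjects: 100 × 0.30 = 30. The exact McNemar test on 30 subjects with cells 0.45 and 0.05 has power 0.89995, as in the table. With 15 and 45 subjects it gives 0.49003 and 0.98561, matching the rows N=50 and N=150. The table is correct, but each entry uses only the true-shunt subjects.

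**2. The same inputs on the detection scale.** Detection rate = prevalence × sensitivity + (1 − prevalence) × (1 − specificity).

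- Perfect specificity: NB-IS 0.3 × 0.9 = 0.270; TTE 0.3 × 0.5 = 0.150; difference 0.120.
- Cited specificities: NB-IS 0.270 + 0.7 × 0.076 = 0.3232; TTE 0.150 + 0.7 × 0.004 = 0.1528; difference 0.1704. False positives supply 0.7 × (0.076 − 0.004) = 0.0504, or 30% of it.

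**3. Power against zero difference on that scale, all subjects.**

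- Perfect specificity: discordant cells 0.3 × 0.45 = 0.135 and 0.3 × 0.05 = 0.015. Power is 0.886 at N=100, 0.897 at N=103 and 0.901 at N=104. The fall from 0.89995 at N=100 arises because the number of shunt subjects now varies instead of being fixed at 30.
- Cited specificities: cells 0.135 + 0.7 × 0.076 × 0.996 = 0.188 and 0.015 + 0.7 × 0.004 × 0.924 = 0.0176. Power is 0.982 at N=100, partly because NB-IS false positives add discordant pairs in its favour.

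**4. What the detection test does with no sensitivity advantage.** Take equal sensitivities and the cited specificities, with discordance D among shunt subjects split evenly. The documents give no D for this case, so it is an assumed range.

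| D | Rejects at N=100 | Rejects at N=150 |
|---|---|---|
| 0.5 | 14% | 21% |
| 0.2 | 22% | 36% |
| 0 | 37% | 71% |

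**5. TEE as the reference.** If every subject had TEE, TEE positives would be 0.3 × 0.95 + 0.7 × 0.05 = 0.32. With perfectly specific NB-IS and TTE, the apparent sensitivities are 0.3 × 0.95 × 0.9 / 0.32 = 0.80 and 0.3 × 0.95 × 0.5 / 0.32 = 0.45. The gap is about 36 points, not 40. The documents give no TEE uptake. If an assumed 30%, 50% or 80% of 100 subjects had TEE, regardless of shunt status and with TEE taken as exact, the plan's own rows N=30, 50 and 80 give power 0.130, 0.490 and 0.799.

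**The case against.** The strongest reply is that TEE is the evident reference: 2.3 calls it the gold standard, and 11.6 sizes a TCD-against-TEE sensitivity estimate at 147 patients. Subjects with TEE can indeed be classified, so it would be wrong to say that true-shunt subjects cannot be identified at all. But the 147 figure concerns the confidence-interval width for TCD alone, and nothing makes TEE the reference for the TCD-TTE difference or ensures that it is done.

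It is also fair that 11.1 puts detection rate and sensitivity under one heading, so the authors may have meant one endpoint. The two coincide only when the denominator is verified shunts, which 4.1 does not require.

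Naming a reference would cure the defect too and would keep the diagnostic-accuracy aim. That stands, and so does the warning that a detection test rewards false positives.

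A reader might go further in three ways that the documents do not support:

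- *That 40% might be relative.* Section 11.6 introduces it after an absolute difference of 51% and computes it as 90% minus 50%. It is absolute; 11.5 only omits the word.
- *That criterion (i) is bound to fail on the detection scale.* The plan never sets 40 points on that scale.
- *That the result could fall anywhere from below zero to far above 40 points, depending on the reference.* The negative case takes TTE as truth, against 11.6. The other wide ranges need TEE referral rates that the documents do not give.

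**Conclusion.** The concern holds. The primary sensitivity comparison lacks an assigned and required reference, and 11.2 contradicts 11.6 by implying TTE as truth. The power arithmetic is sound; the missing element is the way to identify the 30 subjects it uses.

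On the plan's inputs, 40 points of sensitivity correspond to 12 points of detection (27% against 15%) with perfect specificity, or 17 points (32.3% against 15.3%) with the cited specificities. Those figures rest on 30% prevalence and, for the second, on errors independent given shunt status and on NB-IS sharing the cited TCD specificity. That the reference is missing rests on the text alone.

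**What to change.** 1. Align 11.1, 11.5(i) and 11.6 with 4.1. The primary analysis becomes the paired difference in core-lab detection proportion in subjects with both exams, with the McNemar test already planned and a 95% CI. Limit the primary conclusion to detection rate. If the sponsor prefers a sensitivity claim, name the reference, restrict the claim to subjects who have it and restate power for that number.
2. Restate detection-scale power as about 89% at N=100 with perfect specificity, with 104 evaluable subjects needed for 90%. Say that the 98% under the cited specificities is partly due to false positives.
3. State that 40% in 11.5(i) is absolute and refers to sensitivity. Set a detection-scale threshold before core-lab results are linked across modalities.
4. In 11.2, replace the TTE-referenced false-positive, true-negative, false-negative, PPV and NPV lines with positive and negative agreement and discordant counts.
5. Report sensitivity and specificity only against TEE, in subjects who have it, with TEE counts by TTE result, a verification-bias caveat and a note that TEE is itself cited at 95%/95%.

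**Cost.** Text changes and a sponsor decision on the threshold; no added exams. The plan's two 20% inflations give 104 × 1.2 × 1.2 = 149.76, so 150, the Main Study limit in 5.1. The headline difference will be smaller. With equal sensitivities and the cited specificities, the test would still reject 14% to 37% of the time at N=100 and 21% to 71% at N=150, so the result must be shown beside TEE-based specificity.
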